### **2.3.2.3 Primary Efficacy Analyses (ITT)**

The ITT analyses will be performed following the schedule of the per protocol analyses with the only difference being that missing follow-up values will be imputed.

### **2.3.2.4 Sensitivity Analyses (ITT)**

The sensitivity analyses described in the per protocol analyses are not feasible using multiple imputation for computational reasons (bootstrap, random slopes). We plan, however, to use a second imputation model (predictive mean matching) for sensitivity analyses to test the dependency of the results on the concrete imputation method. Thus, we will rerun the ITT analyses only with the

difference that the imputation models (including the same variables as before) will be based on predictive mean matching. Again, 50 runs of imputations will be used.

### **2.3.2.5 Secondary Analyses (ITT)**

The same analyses will be carried out as described in the per protocol analyses with the difference that missing values in the outcome variable at follow-up will be imputed.

## **2.4 Methods against Bias**

Here, we will describe the statistical treatment of potential bias. The methods used in the design of DelpHi-trial to reduce a priori certain kind of bias will be not discussed. Three types of bias need special attention in the DelpHi trial:

- 1) Selection Bias
- 2) Attrition Bias
- 3) Performance Bias

### **2.4.1 Selection Bias**

Although the trial is randomized it is possible that there is selection bias leading to differential baseline values in the primary efficacy outcomes regarding control and intervention group. As the baseline value of the outcome variable is included as covariate in the primary analysis model, the effect sizes of the intervention are thereby independent of baseline differences. Regardless, we will screen the two study group on differences regarding primary and secondary outcome variables, sociodemographic variables and study parameters on differences using generalized linear mixed models with the baseline variable as dependent variable and the study group as predictor. The GP will be included as random effect. The model specification will be specified according the type of variable tested (e.g. logistic for binary variables, Gaussian for metric variables, poisson for count outcomes).

### **2.4.2 Attrition Bias**

We will perform ITT analyses as described to reduce the impact of drop-out during the follow-up interval. To check, whether systematic drop-out during the baseline assessment may influence the results, we will run a drop-out analyses. To this point, we will fit multivariable logistic regressions with drop-out (yes/no) being the dichotomous outcome and the study group, sociodemographic and the screening value of the DEMTECT as predictors. These analyses will be performed three-times:

- 1) Drop-out overall
- 2) Drop-out due to death
- 3) Drop-out due to withdrawal of informed consent

If it would be possible to predict drop-out during baseline by study-group parameters, it would be possible that attrition bias is still present despite the ITT analyses. In this case, the results of the study have to be treated cautiously.

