## **2.3 Efficacy Analyses**

### **2.3.1 Per protocol analyses**

#### **2.3.1.1 Definition of the analyses set**

We define the per protocol analysis as complete case analyses. The only reason not to be included into the per-protocol analysis is due to missing data in the baseline assessment or the follow-up assessment. Contaminations by changing treatment assignments after randomization are impossible due to the study design. The main reason for missing data is supposed to be drop-out because of death or withdrawal of informed consent.

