#### **2.3.2.1 Definition of the Analyses Set**

The ITT analyses will be carried out on the subsample of baseline-sample with baseline data regarding the primary efficacy endpoint under consideration. Thus, individuals which dropped out during the baseline assessment before the efficacy endpoint was surveyed will be excluded from the intention to treat analyses as there is not the necessary data available to allow the imputation of the follow data.

Missing values in the follow-up variable of the primary efficacy outcome will be imputed if the baseline value is not missing. Hence the ITT analyses can be seen as partial ITT analyses. The attrition bias caused by drop-out between the measurement points will be controlled by the imputation. A possible attrition bias caused by drop-out during baseline assessment will be not controlled by the ITT analyses proposed here.

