### **2.3.2.2 Methods of Imputation**

The imputation model will be chosen congenial to the analyses model with the difference that the GP will be included as a fixed effect in the imputation model. Thus, the model of imputation will be a linear regression for the care-giver burden, quality of live and NPI and logistic for antidementive drug use and the PIM, including the respective baseline variable, age, sex, the living status and the study group variable as predictors. The method of imputation is chosen to be multiple imputations via chained equations, using 50 runs of imputations. Standardized effect sizes will be also computed from these imputations and compared to the estimates of the per protocol analyses. Note that an important statistical pre-requisite for the usage of imputations is that the missing of the outcome variable is stochastically independent from the value of the outcome variable at follow-up given its baseline value.

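### Loss between baseline and 12 months is declared controlled by imputation, yet the drop-out models and the caution rule cover only loss during the baseline assessment

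*SAP*

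**What the plan says.** SAP 2.4.2 divides attrition by period. For the follow-up interval it relies on imputation alone: "We will perform ITT analyses as described to reduce the impact of drop-out during the follow-up interval". For the baseline phase it plans three multivariable logistic models (any drop-out, death, withdrawal of consent) with "the study group, sociodemographic and the screening value of the DEMTECT as predictors". Their purpose is stated as: "To check, whether systematic drop-out during the baseline assessment may influence the results, we will run a drop-out analyses". The rule for interpreting them has the same limit: "If it would be possible to predict drop-out during baseline by study-group parameters, it would be possible that attrition bias is still present". Only in that case are the results to be treated with caution.

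SAP 2.3.2.1 states the position on T0-T1 loss without a condition: "The attrition bias caused by drop-out between the measurement points will be controlled by the imputation". SAP 2.3.2.2 then names a prerequisite for imputation, that "the missing of the outcome variable is stochastically independent from the value of the outcome variable at follow-up given its baseline value". It also lists the imputation predictors: baseline outcome, age, sex, living status, study group, and GP as a fixed effect.

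SAP 2.3.1.1 defines the per-protocol set as complete cases: "The only reason not to be included into the per-protocol analysis is due to missing data in the baseline assessment or the follow-up assessment". It expects the losses to come mainly from two sources: "The main reason for missing data is supposed to be drop-out because of death or withdrawal of informed consent".

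**The concern.** The Preliminary Remarks say that attrition bias needs to be assessed and that neither GPs nor participants were blinded. For the baseline phase the plan does assess it. For the 12 months after baseline it substitutes a statement that imputation takes care of it. Both the complete-case estimates and the imputed estimates depend on who is lost in that interval and why.

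Three things follow. The reader will not learn from these analyses whether T0-T1 loss differs by arm or by reason. An observed predictor of loss that is missing from the imputation model would go unnoticed. And the caution rule cannot be triggered by T0-T1 loss, whatever its pattern.

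**Working it through.** The SAP has no figure to reproduce on this point. The check sets its sections side by side.

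**1. Which period do the drop-out models cover?** The sentence before the three-item list in 2.4.2 and the sentence after it both refer to the baseline phase. The first item, drop-out overall, stands beside death and withdrawal, so it most naturally means all reasons, not all periods. No other section models T0-T1 loss or tabulates it by arm.

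**2. When does imputation remove T0-T1 attrition bias?** Only when loss is unrelated to the T1 outcome given the variables conditioned on. SAP 2.3.2.2 names the baseline value alone. Its model also conditions on age, sex, living status, study group and GP, so the working condition is somewhat weaker than the stated one. It is still a condition, and 2.3.2.1 does not carry it.

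**3. Do the planned cross-checks probe the condition?**

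| Planned analysis | Section | Why it does not probe the condition |
|---|---|---|
| Rerun with predictive mean matching | 2.3.2.4 | Changes the way values are drawn and keeps the same variables |
| Imputed versus complete-case effect sizes | 2.3.2.2 | Only the T1 outcome is imputed, from essentially the covariates of the analysis model, so both estimates rest on nearly the same condition and agreement is expected whether or not it holds |

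**4. What kind of loss causes bias?** In a linear model, loss that depends only on included covariates leaves the adjusted arm coefficient unbiased. A simulation under assumed values illustrates this (n = 500, T0-T1 correlation 0.6, no true effect, no clustering):

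- Loss of about 32% versus 22%, rising strongly with baseline severity: adjusted complete-case estimate -0.002 SD (Monte Carlo SE 0.002).
- Loss of 31% versus 22%, with severity acting in opposite directions in the two arms: 0.001 SD (SE 0.002).

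Bias arises when loss is tied to the T1 outcome beyond the covariates. Let p be the fraction lost in an arm and s the distance of the lost patients' true mean from the model's prediction, in SD. The bias in the arm difference then has size |p1 × s1 - p0 × s0|. If the departure is confined to one arm, this is p × s. Over an assumed range:

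| Loss p | s = 0.2 | s = 0.5 |
|---|---|---|
| 10% | 0.02 | 0.05 |
| 20% | 0.04 | 0.10 |
| 30% | 0.06 | 0.15 |
| 40% | 0.08 | 0.20 |

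Every p and s here is an assumption. The table shows how the result would depend on them, not what happened in this trial. The formula also shows that unequal loss is not necessary for bias (s1 and s0 may differ) and not sufficient (both may be zero).

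**5. Is there a concrete candidate variable?** DEMTECT is a predictor in the drop-out models of 2.4.2, so the plan itself regards it as possibly related to loss. It is absent from the imputation predictors in 2.3.2.2. If it predicts both loss and the T1 outcome beyond the listed variables, the condition fails in a way that data already held could reveal and partly repair.

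**The case against.** The strongest reply is that T0-T1 loss is far from ignored. It gets multiple imputation with 50 runs, a second imputation method and a comparison with the complete-case effect sizes. The baseline phase is singled out for good reason, since 2.3.2.1 admits that the ITT analysis cannot cover it. Study group and baseline outcome are in both the analysis and the imputation models, so loss related to arm or baseline severity is already conditioned on. Of the obvious predictors for a T0-T1 drop-out model (study group, age, sex, living situation, DEMTECT, baseline outcome), five of six are in the imputation model. And no drop-out model can test the condition in 2.3.2.2, because the T1 outcome is unobserved in those lost.

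Most of this stands. It means that T0-T1 loss is addressed but not examined, and that drop-out models alone are an incomplete remedy. It does not rescue the unconditional claim in 2.3.2.1, explain why DEMTECT is left out, or supply an analysis under departures from the stated condition. The SAP is limited to efficacy analyses of the primary endpoints, so a descriptive table of loss may exist elsewhere. The caution rule, however, is set here and is confined to the baseline phase.

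A reader might infer that any T0-T1 loss that differs by arm or depends on severity biases both the complete-case and the imputed result. The SAP's models do not support that: such loss is harmless to the adjusted linear estimates if it acts only through the included covariates.

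**Conclusion.** The point holds as a gap in assessment and an overstatement in 2.3.2.1. It does not show that the results are biased. The drop-out models and the caution rule stop at the baseline phase, the claim about T0-T1 attrition depends on a condition that nothing in the plan probes, and one variable the plan itself links to drop-out is left out of the imputation.

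The size cannot be given, because the SAP states no T0-T1 loss rate and no departure from the condition. A reader might set an assumed 0.05 SD against the 0.26 detectable difference for quality of life in Table 1 and report 0.05/0.26 = 19%. The document does not support that ratio: the numerator is wholly assumed and the SAP does not state the unit of 0.26. The change is worth making because it is cheap, and because the primary efficacy models in 2.3.1.2 are first fitted to complete cases, which this loss affects directly.

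**What to change.** 1. In 2.4.2, fit the same three models (any cause, death, withdrawal) to T0-T1 loss, with a GP random intercept and the baseline outcome added to the predictors. Report loss by arm and reason.
2. In 2.3.2.2, add DEMTECT and any other observed baseline predictor of T0-T1 loss to the imputation model as auxiliary variables. The imputed result can then differ informatively from the complete-case result.
3. In 2.3.2.4, add a delta-adjusted imputation: shift the imputed values over a prespecified range, allowing different shifts by arm, and report where the conclusion changes. This covers what drop-out models cannot test.
4. In 2.3.2.1, replace the unconditional statement with one saying that T0-T1 attrition bias is reduced if the condition in 2.3.2.2 holds.
5. Extend the caution rule in 2.4.2 to T0-T1 loss. It should apply when loss is predicted by variables outside the model, or when the result does not survive delta adjustment. Arm imbalance in loss should be reported but should not trigger the rule by itself.

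The cost is a few more models on data already held and a slightly larger imputation model. No new data collection is needed.

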# 1 Preliminary Remarks

The statistical analyses plan was written in its first version in November/Dezember 2015 and was then finalized in March 2016. The follow-up data was analyzed beginning April 2016 until October 2016. Thus, the analysis plan was written before analyzing the follow-up data. However, the baseline data was analyzed since 2013 and the design paper was published in 2011. At the time of the publication of the design paper, the study statistician ([name]) was not yet employed in the DZNE and was therefore neither involved in designing the DelpHi-MV trial, nor in writing the design paper. The statistical analyses plan therefore is not coherent with the design paper in several points. The statistical analyses plan here only describes the efficacy analyses regarding the primary endpoints of the DelpHi trial.

The DelpHi cohort consists of individuals (above 70 years) who were screened positively on dementia. The sampling was done in primary care in the general practice (GP). Additionally, if possible, the principle care giver was included into the study. The GP was randomized by fair coin tossing to care as usual or intervention group. Thus, DelpHi is a cluster randomized clinical trial and all analyses have to respect the stochastic dependency of the data on the GP clustering. The randomization was done before baseline assessment of the individuals and the intervention cannot be classified as blinded, neither on the level of the GP, nor on the level of the study participant. The DelpHi trial can be classified as exploratory as no effect sizes a priori were known for the complex intervention that was performed. Moreover, the trial is clearly a pragmatic trial as it is implemented in primary care. Thus, the internal validity is potentially limited and several sources of bias (especially selection, attrition and performance bias) bias have to be assessed.

The power calculations mentioned in the design paper did not reflect the clustering of the data. The power of cluster randomized trials is not only a function of effect size, significance level and sample size, but dependent on the parameters of the concrete parameters of the clustering which were not known before sampling the data. In general, the power of a cluster randomized trial is lower in comparison to a randomized trial of equal sample size. The concrete loss of power is a function of the

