#### **2.3.1.2 Primary efficacy Analyses**

For primary efficacy analyses, for each of the main outcome of the study a separate generalized linear mixed model is fitted with the model specification corresponding to the scale level of the outcome under investigation. Thus, for quality of life, caregiver burden and neuropsychiatric symptoms linear mixed regressions will be used assuming a Gaussian distribution, while for antidementive drug treatment and PIM prescription logistic mixed models will be used. To account for the stochastic dependency of patients treated by the same GP, the GP will be included as random effect variable.

The follow up outcome variable at  $T_1$  (twelve months after finishing the baseline) will be the dependent variable in these analyses; the study group is the predictor of interest, while the baseline value ( $T_0$ ) of the outcome variable will be included as covariate to diminish residual variance and to account for inter-individual variance at baseline. Furthermore, sociodemographic variables (age, sex and living situation (alone vs. not alone)) are planned to be included as covariates, too. These variables can be supposed to contribute proportions of variance to the outcome variables which should be independent of possible study effects as the intervention cannot change age, sex or living situation. Thus, the inclusion of these variables should result in decreased residual variance enhancing thereby

the statistical power to detect differences between study groups. A positive intervention effect is then defined as a significant regression coefficient (one-sided test) of the study group variable. The p-values will be interpreted one-sided as one-sided hypotheses are tested. The design of the DelpHi trial allows for multiple testing (five primary outcomes), therefore, additionally the Bonferroni corrected p-values will be reported.

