#### **2.5 Post Hoc Power Calculations**

The actual power of the trial was assessed during the baseline sampling when first estimates of the ICCs where known, for reasons explained above. Table 1 gives the estimates for the ICC of the baseline values of the primary efficacy endpoints and the detectable intervention effect (power 80%) given an assumed coefficient of variation of cluster sizes of 1, a baseline follow-up correlation of 0.6,

a mean cluster size of 5 and 100 clusters (GP) included into analysis (total n=500). The power analyses were done with STATA 13/SE using the package *clustersampsi*. Note that the estimates reported in table 1 were derived while the baseline sampling was still ongoing.

**Table 1:** Detectable Difference (power 80%) between Intervention (n=250) and Control group (250)

	Intra-Class Correlation	Detectable Difference	Model
Quality of Life	0.061	0.26	linear
Neuropsychiatric Symptoms	0.361	0.43	linear
Caregiver Burden	0.192	0.35	linear

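### The drop-out models in SAP 2.4.2 test study group with no allowance for GP clustering, so they signal differential drop-out too often if drop-out is correlated within GPs

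*SAP*

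**What the plan says.** Section 1 fixes the unit of randomisation: "The GP was randomized by fair coin tossing to care as usual or intervention group". From this it draws a general rule: "all analyses have to respect the stochastic dependency of the data on the GP clustering".

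Elsewhere the SAP says how the GP enters each model:

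- Primary efficacy models (2.3.1.2), including the logistic mixed models for the two binary outcomes: "To account for the stochastic dependency of patients treated by the same GP, the GP will be included as random effect variable".
- Imputation (2.3.2.2): "the GP will be included as a fixed effect in the imputation model".
- Baseline comparison of the study groups (2.4.1), logistic for binary variables: "The GP will be included as random effect".

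Section 2.4.2 then turns to drop-out during the baseline assessment: "we will fit multivariable logistic regressions with drop-out (yes/no) being the dichotomous outcome and the study group". The other predictors listed are sociodemographic variables and the DEMTECT screening score. The model is fitted three times: for any drop-out, for death and for withdrawal of consent. The GP appears nowhere in this section. A consequence is attached, opening with "If it would be possible to predict drop-out during baseline by study-group parameters": attrition bias may then remain despite the ITT analyses, and the trial's results call for caution.

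**The concern.** Study group is a GP-level variable, so the precision of its coefficient depends on how alike patients of the same GP are. A logistic regression without a GP term treats all patients as independent. If drop-out is correlated within GPs, for instance because some practices keep their patients in the study better than others, the model-based standard error for study group is too small. Confidence intervals are then too narrow and p-values too low.

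Section 2.3.2.1 concedes that the ITT analyses do not control drop-out during baseline, so 2.4.2 is the planned check on that gap. A check that signals too often could attach an unneeded warning to the results.

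**Working it through.** **Inputs from the SAP.** Randomisation by GP (section 1). Planning structure in 2.5: 100 GPs, mean cluster size m = 5, n = 500, coefficient of variation of cluster size CV = 1. The SAP states no figure for the drop-out analysis, so there is nothing to reproduce.

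**Assumptions.** Drop-out ICC of 0.01, 0.05 or 0.10, drop-out rate of 20%, 10% or 3%, and a two-sided 5% test. The ICCs in Table 1 of the SAP (0.061, 0.192, 0.361) belong to outcome scales and are not carried over to drop-out.

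**Step 1, design effect for a GP-level predictor.** DE = 1 + ((1 + CV²)·m − 1)·ICC. With m = 5 and CV = 1 this is 1 + (2·5 − 1)·ICC = 1 + 9·ICC. The correct standard error exceeds the unadjusted one by a factor of √DE.

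**Step 2, true error of a nominal 5% test that ignores clustering.** 2·(1 − Φ(1.96/√DE)). For ICC 0.05: DE = 1.45, √DE = 1.20, 1.96/√DE = 1.63, error 10.4%.

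**Step 3, simulation.** 20,000 trials per setting, 50 GPs per arm, variable cluster sizes (realised CV 0.98, mean n 500), beta-binomial drop-out and no true group effect. The log odds ratio for study group was tested without further covariates. Trials with no event in one arm were left out (under 1%, only at 3% drop-out).

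| Drop-out ICC | DE | √DE | Formula | Simulated, 20% drop-out | 10% | 3% |
|---|---|---|---|---|---|---|
| 0.01 | 1.09 | 1.04 | 6.0% | 6.0% | 5.8% | 4.2% |
| 0.05 | 1.45 | 1.20 | 10.4% | 10.1% | 9.6% | 7.4% |
| 0.10 | 1.90 | 1.38 | 15.5% | 14.9% | 14.7% | 10.8% |

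At 3% drop-out (about 0.03 × 500 = 15 events) the unadjusted test is itself conservative, with an error of about 3.1% when the ICC is near 0. The last column should be read against that value.

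**Step 4, sensitivity.**

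- Equal cluster sizes (CV = 0) give DE = 1 + 4·ICC and errors of 5.5%, 7.4% and 9.8% at the three ICCs.
- A one-sided 5% test at CV = 1 gives 5.8%, 8.6% and 11.6%.
- With ICC = 0 there is no inflation: 5.2% in a separate simulation of 10,000 trials at 20% drop-out.
- Allocating GPs by coin toss instead of 50 per arm changes little: 10.1% and 14.6% at ICC 0.05 and 0.10, with 20% drop-out.

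**Step 5, with the remedy.** In the simulation of step 3, GP cluster-robust standard errors with a t reference on 98 df gave errors of 4.0% to 6.2% across all nine combinations.

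**The case against.** The strongest reply is that 2.4.2 is silent rather than contradictory. It does not exclude a GP effect, and the general rule in section 1 could be read as covering it. That reading is possible, but section 1 says only that clustering must be respected, not how. Where the SAP means a mixed model it says so, and it does so in the sub-section immediately before. An analyst who follows the predictor list in 2.4.2 as written would fit a model that breaks the rule.

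Several other points stand and limit the weight of the finding:

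- The SAP fixes no test level or criterion for prediction. A judgement on the size of the odds ratio alone would not use the standard error; any p-value or interval would.
- The drop-out ICC and rate are unknown. The death and withdrawal models have fewer events than the overall model, so they lie nearer the milder columns of the table.
- The simulation omits the planned covariates, which might absorb some variation between GPs. The planning structure describes patients included in the analysis, not everyone at risk of dropping out during baseline. Neither changes the direction of the error.
- A signal alters no analysis set, model or estimate, and the SAP already warns about attrition in sections 1 and 2.3.2.1.

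**Conclusion.** The concern holds. As written, 2.4.2 departs from the SAP's own clustering rule and yields too small a standard error for study group whenever drop-out is correlated within GPs. Under the planning structure of 2.5 and a two-sided 5% test, the inflation is negligible at a drop-out ICC of 0.01 and clear from about 0.05, where the true error is roughly 10% at drop-out rates of 10% to 20%. It is milder if events are rare or GPs contribute similar numbers of patients, and absent if drop-out does not cluster. These sizes rest on assumed ICCs, drop-out rates and test level.

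The error runs towards false alarms. It does not conceal attrition bias, and the primary efficacy models, which include the GP, are unaffected. The point should be corrected, but it does not threaten the main conclusions.

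**What to change.** State in 2.4.2 that all three drop-out models account for GP clustering. The natural choice is a logistic mixed model with a random GP intercept, as in 2.4.1. Name a fallback, GEE or cluster-robust standard errors by GP, for models in which events such as deaths are too few for the mixed model to be estimated reliably. Fixed GP effects, as used for imputation, would not serve here: study group is constant within a GP, so its coefficient could not be separated from them.

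The cost is one clause and no new data. Intervals become slightly wider, and the mixed model may fail to converge with rare events, which is why the fallback should be named in advance.
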